1.0 Objectives

1.1 **Purpose:** We propose a 100-participant randomized controlled 2-arm parallel trial which employs a metagenomic approach to examine how 8 weeks of supervised moderate-intensity treadmill walking exercise (MWE)^{1,2} for 30-45 min 3 times/week alters the gut microbiome, serum SCFAs, and the cardiometabolic profile, body weight, and body composition of individuals 30-64 years old who are overweight or obese and have PreD.

Aim 1: Compare the effect of 8 weeks of MWE vs. control on shifts in the gut microbiome of overweight or obese individuals with PreD. **H1:** Gut microbial diversity and functional capacity (specifically, genes relevant to SCFA production) will increase improve after 8 weeks in the experimental group vs. control.

Aim 2: Compare the effect of 8 weeks of MWE vs. control on changes in serum SCFAs. **H2:** Serum Levels of SCFAs butyrate, acetate, and propionate will increase after 8 weeks in the experimental group vs. control.

Aim 3: Use formal mediation methods to estimate the proportion of MWE-induced changes in participants' cardiometabolic profiles, body weight, and body composition that are mediated by changes in the gut microbiome and/or serum SCFAs. **H3:** MWE-induced changes in the gut microbiome and serum SCFAs will partly explain changes in participants' cardiometabolic profile (e.g., blood lipids, fasting insulin/glucose, blood pressure, waist circumference), body weight, and body composition.

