3.0 Study Endpoints/Events/Outcomes

3.1 **Primary Endpoint/Event/Outcome:** Expanded data collection procedures for our primary and secondary outcomes are available in Section 5.2. We have two Primary Outcomes. The first primary outcome is changes to the gut microbiome, assessed via metagenomic sequencing, from pre- to post-intervention (**Specific Aim 1**). The Shannon Index—a measure of microbial community diversity with good reproducibility (ICCs>0.50)⁵⁶—will be our primary indicator for changes in gut microbiota composition, and will be assessed at baseline, and following the 4th and 8th weeks. The second primary outcome is serum SCFA levels. Participants will undergo fasted blood draws to assess serum SCFA levels (**Specific Aim 2**). This work will be performed using the Metabolon pipeline.⁵⁷

3.2 **Secondary Endpoint(s)/Event(s)/Outcome(s):** We have several Secondary Outcomes. For **Specific Aim 3** cardiometabolic profiles will be assessed via assays for high-density lipoprotein cholesterol (HDL-C), triglycerides, fasting insulin/glucose, and c-reactive protein (CRP). All blood assays will be conducted by the *UMN Advanced Research and Diagnostic Laboratory* (see ‘Facilities’ document). Blood samples collected will be stored at -80°C prior to batch-processing. Resting blood pressure (BP) will be taken using an Omron Automatic BP Cuff (Omron; Lake Forest, IL), with the average of the last two BP measurements reported. These cardiometabolic indices form the foundation of the ‘metabolic syndrome’,⁵⁹⁻⁶³ and we will form a composite continuous score for cardiometabolic disease risk from HDL-C, fasting glucose, triglycerides, the average of systolic and diastolic BP, and waist circumference. Specifically, z-scores for each biomarker will be calculated and the within-participant average across z-scores computed and referred to as *cardiometabolic disease risk (CMDrisk*; the primary dependent variable for Specific Aim 3). This score has been used in epidemiologic, experimental, and clinical studies.^{62,64-67} Individual components will be described in secondary analyses as needed. We will also measure HbA1c using whole blood analyzed at the UMN Advanced Research Diagnostic Laboratory; the A1cNOW+® device may also be used in a limited capacity to assess validity.⁶⁸ The oral microbiome will be

MEDICAL PROTOCOL (HRP-590)

PROTOCOL TITLE: Exercise and the Gut Microbiome R21

VERSION DATE: 05/11/2022

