5.2 **Study Procedures:** All eligible and consented participants will complete a 3-week run-in phase during which baseline outcome assessments will be performed. During run-in weeks 1 and 2, participants will wear a Fitbit Inspire 2 smartwatch and complete three unannounced dietary recalls. During the run-in week 3 (see table below), participants will consume their 3-day standardized meal plan on days three through five, obtain a fecal sample, and complete a study assessment visit. To quantify compliance with the 3-day meal plan, participants will be provided with a paper checklist of all foods to be consumed, and will be asked to indicate which foods were consumed and to document any deviation. The study assessment visit will include a fasting blood draw, blood pressure in triplicate, weight measure and body fat assessment in duplicate, and a saliva sample. Following successful completion of all measures, participants will then be randomized into one of the two study groups using PROC PLAN (SAS 9.4) and a 1:1 allocation ratio.

Group 1 (Experimental group): Participants will complete 3 treadmill walking sessions/week (24 total sessions) over 8 weeks at or around their home or in-person within the Epidemiology Clinical Research Center. Each walking sessions will be 30 min in duration during intervention weeks 1

MEDICAL PROTOCOL (HRP-590)

PROTOCOL TITLE: Exercise and the Gut Microbiome R21

VERSION DATE: 05/11/2022

through 4 and 45 min during intervention weeks 5 through 8. Notably, this exercise dose (i.e., intensity x session duration x weekly frequency x intervention length) is equivalent to, or greater than, that employed in most existing human studies of exercise and the gut microbiome in addition to the exercise dosage observed necessary to yield meaningful cardiometabolic changes.⁷² Therefore, while the dose is 'modest', it reflects what is relevant in real-world interventions and appropriate for overweight or obese sedentary individuals.

During week 4, participants will again consume their 3-day standardized meal plan, obtain a fecal sample, and complete a study assessment visit (same measures as described above for the 3-week run-in, except no fasting blood draw will be taken).

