The second primary outcome is serum SCFA levels. Participants will undergo fasted blood draws to assess serum SCFA levels (**Specific Aim 2**). This work will be performed using the Metabolon pipeline.⁵⁷ Briefly, serum samples are spiked with a solution of eight stable labelled internal standards and subjected to protein precipitation. After centrifugation, an aliquot of the supernatant is derivatized. The reaction mixture is analyzed by LC MS/MS on an Agilent 1290/ AB Sciex 5500 system. Peak areas of the respective analyte product ions are measured against the peak area of the corresponding internal standard product ions. Quantitation is performed using a weighted least squares regression analysis generated from fortified calibration standards prepared immediately prior to each run.

We have several **Secondary Outcomes**. For **Specific Aim 3** cardiometabolic profiles will be assessed via assays for high-density lipoprotein cholesterol (HDL-C), triglycerides, fasting insulin/glucose, and c-reactive protein (CRP). All blood assays will be conducted by the *UMN Advanced Research and Diagnostic Laboratory* (see 'Facilities' document). Blood samples collected will be stored at -80°C prior to batch-processing. Resting blood pressure (BP) will be taken using an Omron Automatic BP Cuff (Omron; Lake Forest, IL), with the average of the last two BP measurements reported. These cardiometabolic indices form the foundation of the 'metabolic syndrome',⁵⁹⁻⁶³ and we will form a composite continuous score for cardiometabolic disease risk from HDL-C, fasting glucose, triglycerides, the average of systolic and diastolic BP. Specifically, z-scores for each biomarker will be calculated and the within-participant average across z-scores computed and referred to as *cardiometabolic disease risk (CMDrisk*; the primary dependent variable for Specific Aim 3). This score has been used in epidemiologic, experimental, and clinical studies.^{62,64-67} Individual components will be described in secondary analyses as needed. We will also measure HbA1c using standardized procedures and the blood

MEDICAL PROTOCOL (HRP-590)

PROTOCOL TITLE: Exercise and the Gut Microbiome R21

VERSION DATE: 05/11/2022

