15.0 Statistical Considerations

15.1 Data Analysis Plan: Chi-square and independent *t*-tests will evaluate baseline group differences as appropriate. Mediation analyses will also be conducted. We outline our analysis plans in Section 15.3. ⁸⁶⁻⁹²

MEDICAL PROTOCOL (HRP-590)

PROTOCOL TITLE: Exercise and the Gut Microbiome R21

VERSION DATE: 05/11/2022

15.2 Power Analysis: Power for Aim 1 is based on analyses using alpha-diversity (Shannon Index) as the primary outcome. Taniguchi et al.⁴⁶, reported a mean \pm SD baseline Shannon Index of 5.7 ± 0.6 which is consistent with preliminary data from gut samples collected by [name] in other recent projects. Given this variance, and with a balanced design of $n=50$ in the experimental and control arms ($N=100$ total), we will have >99% power to detect a 1 unit increase in Shannon Index. Power for Aim 2 is based on changes in serum SCFAs. Our SCFA assays will be performed at Metabolon and our colleagues at Metabolon provided information on mean \pm SD for these outcomes in their lab. They are as follows: acetate= 1806 ± 2500 ng/mL, butyrate= 35 ± 43 ng/mL, and propionate= 50 ± 52 ng/mL. With these distributions, we will have >80% power to detect a difference in SCFA levels between treatment and control groups with a magnitude of at least 50% of 1 SD.

The primary outcome for Aim 3 will be a composite score based on the average of the z-scores for the following 5 biomarkers: HDL-C, fasting glucose, triglycerides, average of systolic and diastolic BP, and waist circumference. The standardized mean \pm SD of this *CMDrisk* z-score in [name] sedentary behavior intervention among 575 participants (Grant #: R01CA198971) is 0 ± 0.7 . This provides 80% power to detect a difference in the *CMDrisk* z-score of 0.4, between intervention and control at the conclusion of the study.

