Aim 3 analysis: We will use PROC CAUSALMED (SAS 9.4) to explore **mediation** effects on *CMDrisk*. This regression-based model was developed by Valeri and VanderWeele⁹⁹ and VanderWeele.¹⁰⁰ The predictor variable will be treatment (experimental vs. control) and the outcome will be *CMDrisk*. We will include age, *sex as a biological variable*, race/ethnicity, and PA duration as covariates. Mediation will be tested by adding parameters, *in separate models*, for gut microbiota diversity (8-week change in β -diversity) and serum SCFAs (8-week change in levels of serum SCFAs).

15.4 Data Integrity: All data will be double entered separately by two individuals. Blood and stool sample data will be examined for computational value errors associated with out-of-range variables. All data will be examined for outliers and improbable values. More details provided in section 17.1.

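### Aim 3 measures mediator and outcome together at week 8, so the planned mediation model cannot show the direction of effect; a week-4 stool sensitivity analysis would help at little cost

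*Combined protocol and SAP*

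**What the plan says.** Section 1.1 sets Aim 3 as estimating a proportion mediated. H3 expects that "MWE-induced changes in the gut microbiome and serum SCFAs will partly explain changes in participants" and so on through the cardiometabolic profile, weight and body composition.

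Section 15.3, Aim 3, fits PROC CAUSALMED with arm as predictor and CMDrisk as outcome, entering the mediators in separate models. One mediator term is "for gut microbiota diversity (8-week change in" β-diversity); the other is "serum SCFAs (8-week change in levels of serum SCFAs"). Section 15.3 does not date CMDrisk. Section 15.2 does, powering Aim 3 for a "z-score of 0.4, between intervention and control at the conclusion of the study".

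On measurement:

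- Section 15.2 lists the CMDrisk components as "HDL-C, fasting glucose, triglycerides, average of systolic and diastolic BP, and waist circumference". Section 5.2 gives the same list without waist circumference.
- Section 5.2 on SCFAs: "Participants will undergo fasted blood draws to assess serum SCFA levels".
- Section 5.2 on week 4: the run-in measures are repeated, "except no fasting blood draw will be taken".
- Section 3.1 on the Shannon Index: it "will be assessed at baseline, and following the 4th and 8th weeks", so stool exists at all three times. Week-4 stool enters the Aim 1 models in section 15.3, but not Aim 3.
- Table 1 accepts stool on Days 5 to 7, with the assessment visit on Day 7.

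**The concern.** A proportion mediated has its causal meaning only if the mediator changed before the outcome. Randomisation puts exercise before both variables but does not order them against each other. Exercise might improve metabolic state or weight by another route, and that improvement might then alter the gut. The planned model has no lagged mediator and no sensitivity analysis for temporal order, so it would give the same kind of answer in either case. Section 2.1 presents formal mediation as an innovation that will inform the relative importance of the gut microbiome. Direction is therefore central to what Aim 3 is meant to deliver.

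**Working it through.** **1. Timing.** Both mediators use baseline and week 8, and the outcome is at the end of the study. HDL-C, glucose and triglycerides come from the same fasting draw as the SCFAs: 3 of 5 CMDrisk components (sections 3.2 and 15.2) or 3 of 4 (section 5.2). Stool precedes the visit by 0 to 2 days, which cannot order changes built up over 8 weeks.

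**2. The plan's own figure.** Inputs from section 15.2: difference 0.4, SD 0.7, n = 50 per arm. Two-sided alpha of 0.05 is assumed, since the documents do not state it. Power = Φ(0.4 / (0.7 × √(2/50)) − 1.96) = Φ(2.857 − 1.960) = 81.5%; the t-test version gives 80.8%. The stated 80% reproduces. It is power for the total arm effect on CMDrisk, not for a mediated effect.

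**3. Size of a purely reverse artefact.** Let A be arm, Y CMDrisk in SD units and M the mediator, with d = 0.4/0.7 = 0.571 in absolute value. Suppose M has no effect on Y:

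- Y = dA + e
- M = rY + √(1 − r²)u, with e and u independent and of unit variance

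The effect of A on M is rd, and the coefficient of M given A is r. The apparent indirect effect is therefore r²d, the direct effect is d(1 − r²), and the false proportion mediated is r².

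| Assumed r | Total effect | Apparent direct effect | False proportion |
|---|---|---|---|
| 0.3 | 0.571 | 0.520 | 9% |
| 0.5 | 0.571 | 0.429 | 25% |
| 0.7 | 0.571 | 0.291 | 49% |

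Reverse the arrows: M = rdA + v and Y = d(1 − r²)A + rM + √(1 − r²)w. The arm means, variances and within-arm correlation are the same as before, and the proportion mediated is again r², now genuine. The planned data cannot separate the two models.

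**4. At the trial's size.** Simulating the reverse model with N = 100, and calling mediation when both paths (arm to mediator, mediator to outcome) are significant at two-sided 5%, gives a false call in about 12%, 28% and 50% of trials at r = 0.3, 0.5 and 0.7. At r = 0.3 the estimated proportion ranges from about −18% to +40% (central 95%).

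**5. What week-4 stool can do.** Under the same reverse model, with week-4 M and week-8 Y, the artefact becomes r² × ρ × (week-4 effect / week-8 effect), where ρ is the week-4 to week-8 CMDrisk correlation. Assume ρ = 0.5 to 0.8 and a week-4 effect of 0.3 against 0.4, a ratio of 0.75:

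- r = 0.3: 0.09 × 0.75 × (0.5 to 0.8) = 3% to 5%
- r = 0.5: 0.25 × 0.75 × (0.5 to 0.8) = 9% to 15%
- r = 0.7: 0.49 × 0.75 × (0.5 to 0.8) = 18% to 29%

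The artefact falls but does not vanish. In the simulation it vanished only after adjustment for week-4 CMDrisk, which needs a week-4 fasting draw.

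**6. Dose by week 4.** 4 × 3 × 30 = 360 min in weeks 1 to 4 and 4 × 3 × 45 = 540 min in weeks 5 to 8. The share is 360/900 = 40%. Section 4.1 calls 45 min a minimum, so the share could be lower.

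**The case against.** The strongest reply is that this is a limit on interpretation. Section 15.3 speaks of exploring mediation, and CMDrisk sits among the secondary outcomes. A reader might infer that a reverse effect would be reported as mediation and that H3 cannot be answered at all. The documents do not support that. At N = 100 even a purely reverse effect is called mediation in only a minority of trials at r = 0.3 or 0.5, and the 9% artefact is small beside its sampling error. What stands is that a reverse effect could be reported as mediation and that its direction is not identified. Section 1.1 still seeks a proportion, so the word explore does not settle the matter.

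The figures also rest on assumptions. No section gives a mediator-CMDrisk correlation, and r = 0.7 with the whole association reversed is extreme. The algebra takes a signed scalar mediator. Section 15.3 does not say how β-diversity change is scored, and if it is an undirected dissimilarity the r-squared result does not transfer directly. The plan also adjusts for PA duration; if that is on-study activity, it carries part of the treatment effect and the proportion changes again. The percentages are illustrations.

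A reader might also infer that the week-4 and week-8 models should have to agree before mediation is claimed, or that no SCFA proportion should be reported. Neither follows. A purely reverse effect would pass an agreement test in large samples. Under assumed true mediation (mediator effect 0.57 SD, mediator-outcome path 0.5, week-4 to week-8 mediator correlation 0.65), requiring both to be significant cuts detection from about 81% to about 18% if 40% of the mediator effect is present at week 4, and to about 48% if 75% is. Dropping the SCFA proportion would remove part of a stated objective when a clear assumption statement would do.

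Lastly, week-4 blood may be intended after all. Sections 3.2, 7.1, 13.1 and 25.1 still imply it or a third draw, against section 5.2. Even if it were drawn, Aim 3 as written would not use it.

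**Conclusion.** The point holds as a cheap improvement. The Aim 3 model cannot identify whether gut changes drive cardiometabolic changes or follow them. In large samples the artefact is r squared, for example 9% at r = 0.3 and 25% at r = 0.5, under an assumed purely reverse linear model with a signed mediator and no covariates; at N = 100 it is surrounded by wide sampling error. The timing conclusion rests on section 15.2 for the date of CMDrisk and on section 5.2 for the absence of week-4 blood. It does not follow that H3 is unanswerable or that the SCFA analysis should be dropped. A week-4 microbiome mediator would improve the ordering without proving it.

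**What to change.** - **Section 15.3, Aim 3, microbiome:** add a prespecified sensitivity analysis with the baseline-to-week-4 change in the same microbiome mediator that Aim 3 already names and week-8 CMDrisk as outcome. Report it beside the 8-week model, with no rule that the two must agree. State that it reduces reverse causation but does not remove it, because week-4 CMDrisk cannot be formed without a week-4 fasting draw.
- **Section 15.3, Aim 3, serum SCFAs:** keep the planned estimate. Report it as resting on an untestable assumption that the mediator came before the outcome, since both are measured concurrently.
- **Blood schedule:** reconcile sections 3.2, 7.1, 13.1 and 25.1 with section 5.2 on week-4 blood and the number of draws.

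The cost is one extra model on stool already scheduled, some wording, and a weaker causal statement. The week-4 mediator reflects only about 40% of scheduled walking minutes, so the plan should also say that a null week-4 result is not evidence against mediation.

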16.0 Health Information and Privacy Compliance

16.1 Select which of the following is applicable to your research:

My research does not require access to individual health information.

I am requesting that all research participants sign a HIPCO approved HIPAA

Disclosure Authorization to participate in the research (either the standalone form or the combined consent and HIPAA Authorization).

I am requesting the IRB to approve a Waiver or an alteration of research participant authorization to participate in the research.

Appropriate Use for Research:

MEDICAL PROTOCOL (HRP-590)

PROTOCOL TITLE: Exercise and the Gut Microbiome R21

VERSION DATE: 05/11/2022

16.2 Identify the source of Private Health Information you will be using for your research (Check all that apply)

- I will use the Informatics Consulting Services (ICS) available through CTSI (also referred to as the University's Information Exchange (IE) or data shelter) to pull records for me
- I will collect information directly from research participants.
- I will use University services to access and retrieve records from the Bone Marrow Transplant (BMPT) database, also known as the HSCT (Hematopoietic Stem Cell Transplant) database.
- I will pull records directly from EPIC.
- I will retrieve record directly from axiUm / MiPACS
- I will receive data from the Center for Medicare/Medicaid Services
- I will receive a limited data set from another institution
- Other. Describe: N/A

16.3 Explain how you will ensure that only records of patients who have agreed to have their information used for research will be reviewed.

This information will come only from the participants themselves, with all review of any health information occurring in a private room within the Epidemiological Clinical Research Center.

16.4 Approximate number of records required for review: N/A

16.5 Please describe how you will communicate with research participants during the course of this research. Check all applicable boxes

- This research involves record review only. There will be no communication with research participants.
- Communication with research participants will take place in the course of treatment, through MyChart, or other similar forms of communication used with patients receiving treatment.
- Communication with research participants will take place outside of treatment settings. If this box is selected, please describe the type of communication and how it will be received by participants.
Participants will be asked their preferred communication method; if text and/or email is selected, the appropriate consents will be obtained. Diet recalls will be conducted by phone, but only at times provided by study participants.

Participants will be contacted only as it pertains to the study (scheduling/confirming visits, assessing compliance, troubleshooting

MEDICAL PROTOCOL (HRP-590)

PROTOCOL TITLE: Exercise and the Gut Microbiome R21

VERSION DATE: 05/11/2022

technical issues, etc).

Importantly, we will not request access to medical records or any other source of private information about the participants.

16.6 Explain how the research team has legitimate access to patients/potential participants:

Potential participants will make the initial contact with study staff. Only after this initial contact will study staff reach back out to potential participants.

16.7 Location(s) of storage, sharing and analysis of research data, including any links to research data (check all that apply).

In the data shelter of the [Information Exchange \(IE\)](#)

Store Analyze Share

In the Bone Marrow Transplant (BMT) database, also known as the HSCT (Hematopoietic Stem Cell Transplant) Database

Store Analyze Share

In REDCap (recap.ahc.umn.edu)

Store Analyze Share

In Qualtrics (qualtrics.umn.edu)

Store Analyze Share

In OnCore (oncore.umn.edu)

Store Analyze Share

In the University's Box Secure Storage (box.umn.edu)

Store Analyze Share

In an AHC-IS supported server. Provide folder path, location of server and IT Support Contact:

Store Analyze Share

In an AHC-IS supported desktop or laptop.

Provide UMN device numbers of all devices:

Store Analyze Share

Other:

MEDICAL PROTOCOL (HRP-590)

PROTOCOL TITLE: Exercise and the Gut Microbiome R21

VERSION DATE: 05/11/2022

Indicate if data will be collected, downloaded, accessed, shared or stored using a server, desktop, laptop, external drive or mobile device (including a tablet computer such as an iPad or a smartform (iPhone or Android devices) that you have not already identified in the preceding questions

I will use a server not previously listed to collect/download research data

We will monitor participants physical activity using the Fitabase® platform. Fitabase® is a platform provided by Fitbit that allows for research participants to upload their Fitbit smartwatch data each day. We will be able to use this platform and an associated walk log to ensure participants are engaging in their home-based walking. Importantly, Fitabase® houses data in secure, encrypted Microsoft Azure servers and do not sell, release, or otherwise make data available to third parties. Further, we will provide only de-identified participant IDs to Fitabase®, with Fitabase® only having access to de-identified IDs but otherwise unable to access participants' email address or account names.

I will use a desktop or laptop not previously listed

I will use an external hard drive or USB drive ("flash" or "thumb" drives) not previously listed

I will use a mobile device such as an tablet or smartphone not previously listed

